8.3.2. Definition of Serious Adverse Event (SAE)

SAE is defined as an AE or suspected adverse reaction is considered serious if, in the view of either the investigator or the sponsor, it results in any of the following outcomes:

- death,
- a life-threatening AE,
- inpatient hospitalization or prolongation of existing hospitalization,
- a persistent or significant incapacity or substantial disruption of the ability to conduct normal life functions,
- or a congenital anomaly/birth defect.

Important medical events that may not result in death, be life-threatening, or require hospitalization may be considered serious when, based upon appropriate medical judgment, they may jeopardize the patient or subject and may require medical or surgical intervention to prevent one of the outcomes listed in this definition. Examples of such medical events include allergic bronchospasm requiring intensive treatment in an emergency room or at home, blood dyscrasias or convulsions that do not result in inpatient hospitalization, or the development of drug dependency or drug abuse.

'Life-threatening' refers to an AE that at occurrence represents an immediate risk of death

to a subject. An event that may cause death if it occurs in a more severe form is not considered life-threatening. Similarly, a hospital admission for an elective procedure is not considered a SAE.

All SAEs, as with any AE, will be assessed for severity and relationship to study intervention.

All SAEs will be recorded on the appropriate SAE CRF.

All SAEs will be followed through resolution or stabilization by a licensed study physician.

All SAEs will be reviewed and evaluated and will be sent to the SMC (for periodic review), and the IRB/IEC.

8.3.3. Suspected Unexpected Serious Adverse Reactions (SUSAR)

A SUSAR is any SAE where a causal relationship with the study product is at least reasonably possible but is not listed in the Investigator Brochure (IB), Package Insert, and/or Summary of Product Characteristics.

8.3.4. Classification of an Adverse Event

The determination of seriousness, severity, and causality will be made by an on-site investigator who is qualified (licensed) to diagnose AE information, provide a medical evaluation of AEs, and classify AEs based upon medical judgment. This includes but is not limited to physicians, physician assistants, and nurse practitioners.

Severity of adverse events

All AEs and SAEs will be assessed for severity, according to the Division of AIDS (DAIDS) Table for Grading the Severity of Adult and Paediatric Adverse Events, version 2.1 (July 2017).

The following guidelines can be used to determine the severity of AE.

- Mild (Grade 1): Events that are usually transient and may require only minimal or no treatment or therapeutic intervention and generally do not interfere with the subject's usual activities of daily living.
- Moderate (Grade 2): Events that are usually alleviated with additional specific therapeutic intervention. The event interferes with usual activities of daily living, causing discomfort but poses no significant or permanent risk of harm to the research subject.
- Severe (Grade 3): Events interrupt usual activities of daily living, or significantly affects clinical status, or may require intensive therapeutic intervention. Severe events are usually incapacitating.
- Severe (Grade 4): Events that are potentially life threatening.

AEs characterized as intermittent require documentation of onset and duration of each episode. The start and stop duration of each reported AE will be recorded on the appropriate CRF. Changes in the severity of an AE will be documented to allow an assessment of the duration of the event at each level of intensity.

Relationship to Study Intervention

For each reported adverse reaction, the Principal Investigator or designee must assess the relationship of the event to the study product using the following guideline (according to the WHO Master Protocol¹):

- Related - The AE is known to occur with the study intervention, there is a reasonable possibility that the study intervention caused the AE, or there is a temporal relationship

¹ MASTER PROTOCOL. A Multi-centre, Adaptive, Randomized, Double-Blind, Placebo-Controlled Clinical Trial of the Safety and Efficacy of Investigational Therapeutics for the Treatment of COVID-19 in Hospitalized Patients. Electronic source with free access: <https://www.who.int/blueprint/priority-diseases/key-action/multicenter-adaptive-RCT-of-investigational-therapeutics-for-COVID-19.pdf>. Access date: March 13, 2020.

between the study intervention and event. Reasonable possibility means that there is evidence to suggest a causal relationship between the study intervention and the AE.

- **Not Related** - There is not a reasonable possibility that the administration of the study intervention caused the event, there is no temporal relationship between the study intervention and event onset, or an alternate aetiology has been established.

8.3.5. Time Period and Frequency for Event Assessment and Follow-Up

For this study, all Grade 3 and 4 AEs and all SAEs occurring from the time the informed consent is signed through the study completion (end of study) visit will be documented, recorded, and reported.

Investigators Reporting of AEs

Information on all AEs should be recorded on the appropriate CRF. All clearly related signs, symptoms, and results of diagnostic procedures performed because of an AE should be grouped together and recorded as a single diagnosis. If the AE is a laboratory abnormality that is part of a clinical condition or syndrome, it should be recorded as the syndrome or diagnosis rather than the individual laboratory abnormality. Each AE will also be described in terms of duration (start and stop date), severity, association with the study product, action(s) taken, and outcome.

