PROTOCOL TITLE	Open multi-centre study to evaluate efficacy of adding Polyoxidonium® lyophilizate to a complex therapy of hospitalized patients with COVID-19.
STUDY PERIOD	2020
STUDY AIM	To evaluate safety and efficacy of Polyoxidonium® (azoximer bromide) as an

addition to complex treatment of hospitalized patients with COVID-19.

KEY OUTCOMES

EFFICACY OUTCOMES

SAFETY AND EFFICACY

PRIMARY EFFICACY ENDPOINT

Subject clinical status using the WHO 7-point ordinal scale on day 15 as compared to baseline.

1. Not hospitalized, no limitations on activities.
2. Not hospitalized, limitation on activities.
3. Hospitalized, not requiring supplemental oxygen.
4. Hospitalized, requiring supplemental oxygen.
5. Hospitalized, on non-invasive ventilation or high flow oxygen devices.
6. Hospitalized, on invasive mechanical ventilation or ECMO
7. Death.

SECONDARY EFFICACY ENDPOINTS

Clinical severity assessed on scales

1. *Subject clinical status using the WHO 7-point ordinal scale:*
 - Time to improvement of each parameter of the primary scale from admission.
 - Subject clinical status at days 3, 5, 8, 11, and 29.
 - Average change in the clinical status at days 3, 5, 8, 11, 15, and 29 as compared to baseline.
2. *The NEWS Score (National Early Warning Score) describes the vital signs (pulse rate, breathing rate, temperature, blood pressure etc.) and its deviation from the reference ranges): is evaluated daily and on day 15.*
 - The time to discharge or to a NEWS of ≤ 2 and maintained for 24 hours, whichever occurs first.
 - Change from baseline to days 3, 5, 8, 11, 15, and 29 in NEWS.
3. *Oxygenation, including mechanical ventilation:*
 - Change (day by day) in the need for oxygenation in the first 28 days (up to day 29).
4. *Hospitalization*
 - Duration of hospitalization (days).
5. *Mortality (date, cause)*
 - 28-day mortality.
6. *SOFA scale (evaluation of organ failure associated with sepsis): is evaluated daily and on day 15.*
 - Change from baseline to days 3, 5, 8, 11, 15, and 29 in SOFA.

SAFETY OUTCOMES

- Cumulative incidence of serious adverse events/reactions (SAEs, SARs).
- Cumulative incidence of adverse events/reactions (AEs, ARs).
- Permanent or temporary discontinuation of infusions/injections (by any cause).
- Clinically significant changes in the levels of leukocytes, haemoglobin, platelets, creatinine, glucose, total bilirubin, ALT, AST, CRP, and other parameters.

STUDY DESIGN

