4. STUDY DESIGN

4.1. Primary and Secondary Outcomes

According to the aim and objectives of this study, safety and efficacy of Polyoxidonium®, lyophilizate for solution for injections and topical application, 6 mg (NPO Petrovax Pharm LLC, Russia) will be evaluated in hospitalized patients with coronavirus disease (COVID-19).

Efficacy outcomes

Primary efficacy outcome

Subject clinical status using the WHO 7-point ordinal scale on day 15 as compared to baseline.

1. Not hospitalized, no limitations on activities.
2. Not hospitalized, limitation on activities.
3. Hospitalized, not requiring supplemental oxygen.
4. Hospitalized, requiring supplemental oxygen.
5. Hospitalized, on non-invasive ventilation or high flow oxygen devices.
6. Hospitalized, on invasive mechanical ventilation or ECMO.
7. Death.

Secondary efficacy outcomes

Clinical severity assessed by scales

1. Subject clinical status using the WHO 7-point ordinal scale

- Time to improvement of each parameter of the primary scale from admission.

- Subject clinical status at days 3, 5, 8, 11, and 29.
 - Average change in the clinical status at days 3, 5, 8, 11, 15, and 29 as compared to baseline.
2. *The NEWS Score (National Early Warning Score) describes the vital signs (pulse rate, breathing rate, temperature, blood pressure etc.) and its deviation from the reference ranges):* is evaluated daily and on day 15.
- The time to discharge or to a NEWS of ≤ 2 and maintained for 24 hours, whichever occurs first.
 - Change from baseline to days 3, 5, 8, 11, 15, and 29 in NEWS.
3. *Oxygenation, including mechanical ventilation:*
- Change (day by day) in the need for oxygenation in the first 28 days (up to day 29).
4. *Hospitalization*
- Duration of hospitalization (days).
5. *Mortality (date, cause)*
- 28-day mortality.
6. *SOFA scale (evaluation of organ failure associated with sepsis):* is evaluated daily and on day 15.
- Change from baseline to days 3, 5, 8, 11, 15, and 29 in SOFA.

Safety outcomes

Safety outcomes

- Cumulative incidence of serious adverse events/reactions (SAEs, SARs)
- Cumulative incidence of adverse events/reaction (AEs, ARs)
- Permanent or temporary discontinuation of infusions/injections (by any cause)
- Clinically significant changes in the levels of leukocytes, haemoglobin, platelets, creatinine, glucose, total bilirubin, ALT, AST, CRP, and other parameters.

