8.3. Recording and reporting of adverse events

8.3.1. Definition of Adverse Event (AE)

Adverse event means any untoward medical occurrence associated with the use of an intervention in humans, whether considered intervention related or not. An AE can therefore be any unfavourable and unintended sign (including an abnormal laboratory finding), symptom, or disease temporally associated with the use of medicinal (investigational) product.

Any medical condition that is present at the time that the subject is screened will be considered as baseline and not reported as an AE. However, if the severity of any pre-existing medical condition increases, it should be recorded as an AE.

Given the nature of severity of the underlying illness, subjects will have many symptoms and abnormalities in vitals and laboratory. All Grade 3 and 4 AEs will be captured as AEs in this study.

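### Section 8.3.5 gives two AE recording rules, Grade 3-4 plus SAEs and then all AEs, and the ungraded AE incidence outcome depends on which one a site follows

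*Combined protocol and SAP*

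**What the plan says.** All references are to the combined protocol and SAP.

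- **8.3.5, first sentence:** "all Grade 3 and 4 AEs and all SAEs occurring from the time the informed consent is signed", up to the study completion visit, "will be documented, recorded, and reported".
- **8.3.5, next paragraph, on investigators' reporting:** "Information on all AEs should be recorded on the appropriate CRF".
- **8.3.1:** after noting that "subjects will have many symptoms and abnormalities in vitals and laboratory", it states "All Grade 3 and 4 AEs will be captured as AEs in this study". SAEs are not mentioned in that sentence. The AE definition in the same section has no grade threshold. Conditions present at screening count as baseline, but "if the severity of any pre-existing medical condition increases, it should be recorded as an AE".
- **8.3.4:** every AE and SAE is graded, and Grades 1 and 2 are defined.
- **6.3.9:** AE recording follows Section 8; no rule of its own is given.
- **Synopsis, 4.1 and 8.1:** the safety outcome is cumulative incidence of AEs and adverse reactions, without a grade limit.
- **9.7.3:** the number of patients with any AE will be presented, together with AE counts for each severity category and by causal relationship.

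**The concern.** The first sentence of 8.3.5 covers documenting and recording as well as reporting. The two statements therefore cannot be reconciled by saying that everything is recorded and only severe events are reported. One sentence sets a Grade 3-4 or serious threshold for the CRF; the next paragraph sets none.

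Safety is one of the two objectives in 3.2, and 11.9 commits the final report to a conclusion on the safety profile. AE incidence is one of the listed outcomes behind that conclusion. If sites apply the narrow sentence, the reported incidence omits most patients whose only events were non-serious and Grade 1-2. The Grade 1-2 counts under 9.7.3 would then hold little beyond low-grade SAEs and worsened pre-existing conditions. Section 4.3 foresees many centres in several countries, so sites may resolve the ambiguity differently, and differences in AE rates between them could reflect the recording rule alone. Section 9.4 rules out substituting missing data, so an event that never reaches the CRF is not recovered at analysis.

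**Working it through.** The plan states no figure on this point, so there is nothing to reproduce. The check is first textual; the arithmetic then shows scale only.

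**Step 1. Try each reading against the text.**

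| Reading | Conflict or gap |
|---|---|
| Threshold: only Grade 3-4 AEs and SAEs are recorded | Contradicts the all-AEs sentence in 8.3.5 and the ungraded rule in 8.3.1 for worsened conditions; the outcome name in the synopsis, 4.1 and 8.1 claims more than is collected; Grade 1-2 counts in 9.7.3 are nearly empty |
| "Information on all AEs should be recorded on the appropriate CRF" means all AEs already captured under the first sentence | Not stated; same mislabelled outcome; at odds with the ungraded AE definition |
| Floor: Grade 3-4 and SAEs at least, and all others too | Possible, since neither sentence restricts itself expressly; but the Grade 3-4 sentences then add nothing to what is recorded, and the remark in 8.3.1 about many symptoms points to a threshold |

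Every reading needs an edit. The Grade 1-2 definitions in 8.3.4 fit all-grade capture but do not prove it, because an SAE can be low grade.

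**Step 2. Formula for the loss in recorded incidence.**

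Inputs, none of them given in the documents:
- H: share of patients with a Grade 3-4 AE, an SAE or a worsened pre-existing condition.
- L: share whose only AEs are non-serious Grade 1-2 events other than a worsened pre-existing condition.
- s: share of patients at sites using the narrow rule, with L assumed equal at both kinds of site.
- r: share of patients so missed who are retrieved from source before analysis.

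True incidence = H + L. Recorded incidence = H + L − s × L × (1 − r). Loss = s × L × (1 − r), which runs from 0 (s = 0 or r = 1) to L (s = 1, r = 0).

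**Step 3. Scale fixed by the sample size.** The synopsis plans at least 50 patients. One patient missed = 1/50 = 2.0 percentage points. The divisor is the safety population (9.6, 9.7.3), so the figure is smaller if more are treated and larger if fewer than 50 are.

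**Step 4. Illustration, on assumed values.** Write L = q × w, where q is the share of patients with any AE and w the share of those patients who fall in L.

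- q = 40%, w = 50%: L = 0.40 × 0.50 = 20%. Among 50 patients, full capture shows 20 with an AE; the narrow rule everywhere shows 10.
- At L = 20% and r = 0: s = 0, 25, 50, 100% gives a loss of 0, 5, 10, 20 points.
- At L = 20%, s = 50%, r = 50%: 0.50 × 20 × 0.50 = 5 points.
- Over q = 20-60% and w = 25-90%, L runs from 0.20 × 0.25 = 5% to 0.60 × 0.90 = 54%. That is the worst-case loss (s = 1, r = 0) at each end.

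**Step 5. What this is not.** The point is not about detecting labelled reactions. At the labelled frequency for local reactions (1/1000 to 1/100, Sections 2.2 and 2.4.2), 50 patients give an expected 50 × 0.001 = 0.05 to 50 × 0.01 = 0.5 cases.

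**The case against.** The best counter-argument is that the Grade 3-4 sentences set a floor. The first sentence of 8.3.5 stands under a heading about time period and frequency and mainly sets a window. The sentence in 8.3.1 can mean that severe events count as AEs even when COVID-19 might explain them. The instruction in 8.3.5 that names the CRF is ungraded. That reading is open, but the protocol does not state it, and a site reading the opening sentence of 8.3.5 literally would not be at fault.

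A second argument is that the gaps would be caught. Section 13.2 lists adverse events among source data without a grade limit, 9.10 and 11.3 have monitors compare the CRF with source, and 8.1 asks investigators to notify the Sponsor of anything unusual. Some missed events might well be recovered. But a monitor who reads 8.3.5 restrictively has no reason to query an absent Grade 1-2 event, and the duty in 8.1 is not a CRF rule.

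A third argument is that the size is unknown and may be nil. This stands. The eCRF instructions and monitoring plan are not in the documents, and either could settle the matter in practice. There is also no comparator arm to bias, and many added low-grade entries would reflect the disease. These points limit the consequence; they do not remove the contradiction.

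**Conclusion.** The concern holds. The capture rule is internally inconsistent, and a listed safety outcome and the planned severity counts depend on how it is read. That conclusion rests on the wording alone and not on any assumed rate.

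The size is not computable from the documents. It ranges from no loss up to L, at 2.0 points per missed patient when 50 are analysed; every figure in Step 4 rests on assumed inputs. The formula covers the patient-level incidence. The event counts by severity in 9.7.3 would also fall, by an amount that cannot be derived. SAE incidence, discontinuation of injections and laboratory changes are unaffected. This should be corrected, but it does not invalidate the study.

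**What to change.** **Preferred.** Reword 8.3.1 and 8.3.5 into one rule: AEs of every grade go on the CRF from informed consent to the end-of-study visit, with conditions present at screening treated as baseline unless they worsen. This matches the outcome and the 9.7.3 presentation as they stand. The cost is wording in two sections and more AE entries for at least 50 patients. Table 1 already schedules safety assessment daily to discharge and at later visits. The downside is a higher reported AE rate, with many entries reflecting COVID-19 in a single group.

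**Alternative.** Keep the Grade 3-4 threshold and change the all-AEs sentence of 8.3.5. Then rename the outcome in the synopsis, 4.1 and 8.1 and the presentation in 9.7.3 to the events actually captured, and state that AE and AR incidence excludes most non-serious Grade 1-2 events. Section 8.3.1 should be aligned too, since its Grade 3-4 sentence omits SAEs. This touches more places and gives up low-grade incidence.

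A compromise that keeps only related low-grade events would not work with the current definition in 8.3.4. A temporal relationship alone satisfies it, so it would filter little while dosing runs from day 1 to day 17.

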8.3.6. Serious Adverse Event Reporting

Investigators Reporting of SAE s

Any AE that meets a protocol-defined criterion as a SAE must be submitted immediately (within 24 hours of the centre awareness) on an SAE form to the designated Pharmacovigilance Group, at the following address:

NAME	[name]
POSITION	Pharmacovigilance manager
COMPANY	NPO Petrovax Pharm LLC
ADDRESS	[name]
[contact]
EMAIL	[contact]

Other supporting documentation of the event may be requested by the designated Pharmacovigilance manager and should be provided as soon as possible. The designated Medical Monitor will review and assess the SAE for regulatory reporting and potential impact on study subject safety and protocol conduct.

At any time after completion of the study, if the centre PI or appropriate study doctor becomes aware of an SAE, they will report the event to the designated Pharmacovigilance Group.

Reporting SAEs to regulatory authorities

Following notification from the centre PI or appropriate sub-investigator, the Sponsor will report any SUSAR in an IND safety report to the regulatory authority and will notify all PIs of the participating centres as soon as possible. Any unexpected fatal or life-threatening suspected adverse reaction will be reported to the regulatory authority as soon as possible, but in no case later than 7 calendar days after the sponsor's initial receipt of the information. If the event is not fatal or life-threatening, the safety report will be submitted within 15 calendar days after the sponsor determines that the information qualifies for reporting. Relevant follow up information to an IND safety report will be submitted as soon as the information is available.

Upon request from regulatory authority, the sponsor will submit any additional data or information that the agency deems necessary, as soon as possible, but in no case later than 15 calendar days after receiving the request.

SAEs that are not SUSARs will be reported to the regulatory authority at least annually in a summary format which includes all SAEs.

Centres may have additional local reporting requirements (to the IRB and/or national regulatory authority).

8.3.7. Reporting Events to Subjects

Subjects will be informed of any severe AEs or SAEs that occur as part of their participation in this study.

8.3.8. Reporting of Pregnancy

Pregnancy is not an AE. However, any pregnancy that occurs during study participation should be reported to the sponsor and recorded on the appropriate CRF. Pregnancy should be followed to the outcome.

8.4. Unanticipated Problems

8.4.1. Definition of Unanticipated Problems

An Unanticipated Problem is any event, incident, experience, or outcome that meets the following criteria:

- Unexpected in terms of nature, severity, or frequency given (a) the research procedures that are described in the protocol-related documents, such as the approved study protocol and informed consent document; and (b) the characteristics of the subject population being studied;
- Related or possibly related to participation in the research ('possibly related' means there is a reasonable possibility that the incident, experience, or outcome may have been caused by the procedures involved in the research); and
- Suggests that the research places subjects or others at a greater risk of harm (including physical, psychological, economic, or social harm) than was previously known or recognized.

8.4.2. Unanticipated Problem Reporting

To satisfy the requirement for prompt reporting, unanticipated problems (UP) will be reported using the following timeline:

- UPs that are SAEs will be reported to the Statistical and Data Coordinating Centre (SDCC)/study sponsor and the ethics committee within 24 hours of the investigator becoming aware of the event per the above describe SAE reporting process.
- Any other UP will be reported to the SDCC/study sponsor and the ethics committee within 3 days of the investigator becoming aware of the problem.

